	
 
Endodontic Assessments including Periradicular Tests (Percussion and Palpation), Cold Test, Root Resorption, Pulp Diagnosis, and Periradicular Diagnosis
 

	
 
Procedural details including Calcification Assessment, Irrigation, and Material Utilization
 

	Sonendo GentleWave System Devices Utilized
	Traditional Root Canal Therapy Devices and Instruments Utilized
	Procedure Time (dental dam placement to removal)
	Sonendo GentleWave Treatment Time (Treatment Time)
	Cone Beam Computed Tomography (CBCT) Sub-Set Evaluation
	Radiographic Evaluation of Obturation
	Adverse Events
Questionnaires	The following questionnaires will be completed for the study:
Completed for the Study	
 
McGill Short Form Pain Questionnaire at Baseline, 1, 2, 3, 7 and 14 days post-procedure, at all Follow-up Visits and at Unscheduled Visits, as necessary
 

•	Gracely Descriptor Differential Scale (DDS) at Baseline, immediately post procedure and 1 day post procedure
•	Patient Satisfaction Survey immediately post procedure
•	AAE Case Difficulty Assessment post procedure

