#### 7.4.4 Baseline Exam

The PI will perform the following standard of care assessments and evaluations prior to the procedure, if they were not already completed:

- 1. Medical and Dental History and Exam
  - a. Medical History: Only those histories related to endocrine/metabolic, hematologic, musculoskeletal, and immunological will be collected for the study.
- 2. Medication Regime: Only prescribed herbal or over the counter systemic antibiotics, analgesics, and anti-inflammatory medications taken during the duration of the study (24 months post procedure) and the prior three months will be documented for this study.
  - Any antibiotics, analgesics or anti-inflammatory medications provided intraprocedure by the PI during the Baseline and Procedure Visits will be collected for the study and will be documented on the Concomitant Medication Log.
  - Any antibiotics, analgesics and anti-inflammatory medications should be collected if prescribed or provided post Procedure Visit, and at all Follow-ups.
- 3. McGill Short Form Pain Questionnaire: The McGill Pain Questionnaire (MPQ) is one of the most widely used tests for the measurement of pain. It provides information on sensory, affective, and evaluative dimensions of pain experience and is capable of discriminating among different pain problems.

- 4. Gracely Descriptor Differential Scale (DDS): This scale is an intensity and unpleasantness scale. The scale includes both verbal and numeric characteristics.
- Diagnostic Radiographic Analysis: Periapical (PA) Parallel Radiograph, showing the periapical region surrounding the subject tooth should be collected for each visit. Additional radiographs completed as necessary by the PI will be collected for the study.
- 6. Periapical Index (PAI) Score analyzed by independent reviewer Up to three (3) independent reviewers will be provided radiographs in order to complete the PAI scoring. Independent reviewers will be blinded to the site, subject, and visit when completing the PAI score. This is being done to eliminate bias.
  - Score of 1: Normal
  - Score of 2: Small changes in bone structure
  - Score of 3: Changes in bone structure with some mineral loss (bone loss)
  - Score of 4: Periodontitis with well-defined radiolucent area (apical periodontitis)
  - Score of 5: Severe Periodontitis with exacerbating features (apical periodontitis)

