    - Asymptomatic Apical Periodontitis: Inflammation and destruction of apical periodontium that is of pulpal origin, appears as an apical radiolucent area, and does not produce clinical symptoms.
    - Acute Apical Abscess: An inflammatory reaction to pulpal infection and necrosis characterized by rapid onset, spontaneous pain, tenderness of the tooth to pressure, pus formation, and swelling of associated tissues.
    - Chronic Apical Abscess: An inflammatory reaction to pulpal infection and necrosis characterized by gradual onset, little or no discomfort, and the intermittent discharge of pus through an associated sinus tract.

• Condensing Osteitis: Diffuse radiopaque lesion representing a localized bony reaction to a low-grade inflammatory stimulus, usually seen at apex of tooth.

After assessments are completed, the patient may be prescribed medication(s) for pain management according to standard of care procedures. If analgesic medications need to be provided to the patient in order to complete one or more of the assessments, the assessments that require a pain response (i.e. cold test, percussion and palpation) should be completed prior to providing these medications.

Upon determining that the patient meets all the Pre-Procedure Inclusion and none of the Pre-Procedure Exclusion Criteria, the patient may proceed to the Procedure Visit.

If the patient does not meet all of the Pre-Procedure Inclusion and/or meets any of the Pre-Procedure Exclusion Criteria, the patient will be considered a Screen Failure (see Section 7.6.1 Screen Failures).

All redacted source documentation with PI signature should be provided to the Sponsor for filing after each study visit. If changes are made to the source documents after PI signature, the updated source documents should be provided to the Sponsor for filing.

Both Screening Dentists and PIs conduct a medical and dental review and assessments on a patient. The Screening Dentist performs this review only as part the pre-screening process. Information collected by a Screening Dentist will not be included as study data (i.e. Screening Form, pre-screening radiographs, and dental notes). Only information collected by a PI will be used as study data. The data collected or assessments performed by a PI supersede those completed by a Screening Dentist. Source data verification will occur using the subject's dental file.

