## 7.5.2 Root Canal Therapy Procedure Preparation

During RCT preparation, the PI should assess the subject tooth to determine if the tooth meets all of the Intra-Procedure Inclusion and none of the Intra-Procedure Exclusion Criteria. The RCT preparation is to be performed using standard endodontic practices.

- 1. Use of a dental bib is recommended.
- 2. Protective safety eyewear is required.
- 3. Anesthetize the subject tooth and surrounding area.

Note: If at any stage throughout RCT preparation, the subject expresses pain, sensitivity or discomfort, the PI may provide more anesthetic per standard practice.

- 4. Isolate the subject tooth by placing a rubber dam.
- 5. If using an Occlusal Plate, it is recommended to clamp the distal adjacent tooth, if a distal adjacent tooth is present. If using a Tooth Cap, it is recommended to clamp the subject tooth.
- 6. Use of a putty or caulking (i.e. OraSeal® (Ultradent) or equivalent) along the subject tooth and rubber dam interface for optimum isolation of the subject tooth is recommended.
- 7. The subject tooth may be disinfected (e.g. using chlorhexidine or betadine).
- Any caries and/or dental fillings (e.g. amalgam) on the subject tooth must be removed.
  If a crown, inlay or onlay is present, it does not require removal unless necessary for treatment or if caries and/or leakage are present below the crown, inlay or onlay.

Note: If there is tissue present that may affect caries removal and/or crown restoration, sear off the tissue according to standard dental practice.

9. Use of caries detector to ensure that all caries are removed even if caries are not visibly present or cannot be detected with a dental probe is recommended.

Note: Ensure that the tooth is restorable without a post and has adequate biological width for restoration after caries removal. If not, the patient will be considered a Screen Failure (see Section 7.6.1 Screen Failures).

10. When necessary, restore/build-up the missing subject tooth structure with permanent restorative and bonding materials. Ensure the permanent restorative material is fully cured prior to treatment with the GentleWave System.

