- Acute Apical Abscess: An inflammatory reaction to pulpal infection and necrosis characterized by rapid onset, spontaneous pain, tenderness of the tooth to pressure, pus formation, and swelling of associated tissues.
- Chronic Apical Abscess: An inflammatory reaction to pulpal infection and necrosis characterized by gradual onset, little or no discomfort, and the intermittent discharge of pus through an associated sinus tract.
- Condensing Osteitis: Diffuse radiopaque lesion representing a localized bony reaction to a low-grade inflammatory stimulus, usually seen at apex of tooth
- 8. Adverse Events (see Section 10.0 Adverse Event).

After assessments are completed, the patient may be prescribed medication(s) for pain management according to standard of care procedures. If analgesic medications need to be provided to the patient in order to complete one or more of the assessments, the assessments that require a pain response (i.e. cold test, percussion and palpation) should be completed prior to providing this medication.

All redacted source documentation with PI signature should be provided to the Sponsor for filing after each study visit. If changes are made to the source documents after PI signature, the updated source documents should be provided to the Sponsor for filing.

In addition, the clinical site designee will report all significant findings at Follow-Up Visits to the Sponsor either via email or by sending redacted source documentation.

Subjects should be evaluated to determine if the subject tooth remains functional. If the subject tooth is or still requires healing, the subject should be evaluated closely. If the subject has clinical symptoms or signs after the twelve month follow-up, the PI should follow standard endodontic care, as applicable. All such care should be documented accordingly for the study.

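### The rule that puts pain tests before analgesics leaves out the McGill and the DDS, and one of three DDS readings is taken when local anaesthetic may still be acting

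*Combined protocol and SAP*

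**What the plan says.** The Baseline Exam (7.4.4) opens with "The PI will perform the following standard of care assessments and evaluations prior to the procedure, if they were not already completed". The McGill is item 3 on its list and the DDS is item 4. After the list comes the default order: "After assessments are completed, the patient may be prescribed medication(s) for pain management according to standard of care procedures". The next sentence covers the exception, in which an analgesic is needed to get through an assessment. There, "the assessments that require a pain response (i.e. cold test, percussion and palpation) should be completed prior to providing these medications".

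Section 7.17.2 carries the same default and the same exception for follow-up visits: "the assessments that require a pain response (i.e. cold test, percussion and palpation) should be completed prior to providing this medication". Its assessment list has the McGill as item 2. It has no DDS and no cold test.

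The synopsis sets the timing of the two questionnaires: "Gracely Descriptor Differential Scale (DDS) at Baseline, immediately post procedure and 1 day post procedure" and "McGill Short Form Pain Questionnaire at Baseline, 1, 2, 3, 7 and 14 days post-procedure, at all Follow-up Visits and at Unscheduled Visits, as necessary". The schedule in section 8.0 agrees. Step 3 of the procedure preparation in 7.5.2 is "Anesthetize the subject tooth and surrounding area", and a note there allows more anaesthetic if the subject has pain.

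The McGill and the DDS are the first two secondary endpoints in section 3.3. Section 13.5 gives only the timing of the secondary analysis, and section 13.0 leaves the details of the methods to the statistical analysis plan.

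**The concern.** The exception rule accepts that a pain response should be captured before an analgesic, but applies this to three chairside tests only. A site that follows the text exactly could collect a self-reported pain score after the drug. The patients concerned are those in enough pain to need an analgesic to be examined. A medicated Baseline score would understate their starting pain, and a medicated follow-up score would understate their remaining pain.

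The follow-up list seems not to have been matched to its visit, since it protects a cold test that 7.17.2 does not list and omits the McGill that it does.

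The immediate DDS raises a different problem, and one that applies to almost every subject. Post-procedure pain is part of the objective in the synopsis and is to be compared with a literature control. The study has one arm, so no concurrent group shares the anaesthetic effect and cancels it. With no pain analysis specified, a fall from Baseline to the immediate reading could be reported as an effect of treatment.

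**Working it through.** The plan gives no figure for any pain measure, so there is no pain figure to reproduce. The check compares the text section by section and counts readings.

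**1. What the exception rule covers**

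- Baseline (7.4.4): the rule names cold test, percussion and palpation. The visit also collects the McGill and the DDS, and neither is named.
- Follow-up (7.17.2): the rule names the same three tests. The visit lists percussion, palpation and the McGill. The McGill is not named, and the cold test is named without being listed.
- Both lists are introduced by i.e. and not e.g., so they read as complete.

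**2. Which readings are exposed to the rule**

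- McGill: 1 Baseline + 5 out-patient (days 1, 2, 3, 7, 14) + 4 follow-up visits (months 6, 12, 18, 24) = 10 scheduled readings. The rule can bear on 1 + 4 = 5 of them. The 5 out-patient readings lie outside any clinic ordering rule.
- DDS: Baseline, immediately post procedure and day 1 = 3 readings. The rule can bear on the Baseline reading only.

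**3. Which readings directly follow the anaesthetised procedure**

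- DDS: 1 of 3 readings, and so 1 of the 2 changes from Baseline that could be formed.
- McGill: 0 of 10 scheduled readings.

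**4. Whether recorded drug data could separate the effects later**

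- Sections 7.4.4 and 7.13 log antibiotics, analgesics and anti-inflammatories given at the Baseline and Procedure Visits. Local anaesthetic is not named among them.
- Section 7.14 documents drugs prescribed after the procedure at the next study visit, if they were taken. The first follow-up visit is at 6 months (7.17).
- No item asks whether an analgesic was taken on the day a questionnaire was completed.

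**5. Whether the primary sample size is touched**

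Section 13.1 claims about 90% power with 86 evaluable subjects, 85% against 70%, in a two-sided 5% binomial test. The exact test rejects in favour of the device at 69 or more responders, with an upper-tail error of 0.0223 and a power of 0.914. The claim reproduces, and 108 × 0.8 = 86.4 agrees with the stated number. No pain score enters this calculation.

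**The case against.** The strongest reply is that the default already protects the questionnaires. Both sections place prescribing after the assessments, and the McGill and DDS are among those assessments. This stands, and it confines the ordering gap to cases where an analgesic is needed to complete an assessment. A reader might infer that Baseline pain is routinely scored under medication. The text does not support that.

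It can also be said that analgesics are already recorded. That is true, but not on a time scale that links them to a given form.

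The mismatch over the cold test is softened because the intra-oral examination in 7.17.2 is described as open-ended. The omission of the McGill is not softened by this.

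The immediate DDS is not worthless. It describes the patient's state on leaving and sits beside a satisfaction survey that asks about sensations during the procedure. It is a poor basis for a change from Baseline, and no more than that is claimed. The day 1 DDS can itself be affected by analgesics taken after the procedure, which is why same-day use has to be recorded with it.

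Finally, the plan defines no pain change score. Contamination of such a score is therefore a risk left open by an unspecified analysis, and not a fault in a planned one.

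**Conclusion.** The point holds in a limited form. The exception rule omits the McGill at Baseline and follow-up and the DDS at Baseline, so exact compliance can yield medicated pain scores in the exception cases. One of three DDS readings is taken when local anaesthetic may still be acting. This rests on the assumption that some effect can outlast the procedure, since the documents give no duration.

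Neither effect can be sized. A reader might multiply an assumed 10–30% of subjects medicated by an assumed drop of 1–3 points and get a mean shift of 0.10 × 1 = 0.1 to 0.30 × 3 = 0.9 points. Both inputs are invented, and the only 0–10 scale described is the rating for telephone or mail contact in section 7.19, so the result does not carry over to the McGill or the DDS.

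A reader might also infer that a medicated score could turn a symptomatic tooth into a healed one. The documents do not support this. Nothing feeds the McGill or DDS into the healed or healing classification, the DDS ends at day 1, and percussion and palpation are already protected.

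The matter concerns the first two secondary endpoints. It is worth correcting because correction is nearly free, but the primary result is not shown to be at risk.

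**What to change.** - **Section 7.4.4:** add the McGill and the DDS to the assessments to be completed before an analgesic is given.
- **Section 7.17.2:** add the McGill only, since the DDS is not collected at these visits. In the same edit, reconcile the cold test with the visit's assessment list.
- **Both additions** govern the order of forms only. They leave decisions on medication as they are.
- **Every McGill and DDS form:** add one item asking whether an analgesic was taken that day.
- **Section 13.5:** state that the day 1 reading is the post-procedure DDS, reported with same-day analgesic use. State that the immediate reading is descriptive only and is labelled as taken after local anaesthesia.

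The cost is one extra data item, two short wording changes and one analysis statement, with no added visit or procedure. Form order does nothing for the out-patient McGill readings on days 1 to 14. For those, the same-day analgesic item is the only part of the fix that helps.

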# 7.4.5 Baseline Exam Re-Assessment

For most patients, the Baseline and Procedure Visits will be on the same day. The patient and/or PI may choose to have the Procedure Visit occur on a day separate than that of the Baseline Visit.

If the Procedure Visit is not on the same day as the Baseline Visit, the Procedure must occur within seven (7) days. If the Procedure Visit is not completed within seven (7) days of the Baseline Visit, the Baseline Exam results are no longer valid and must therefore be repeated and captured on a new source document. Only data captured on the final Baseline Visit will be used for data analysis and will be monitored. All assessments listed under *Section 7.4.4 Baseline Exam* need to be repeated if the Procedure Visit is not completed within seven (7) days of the Baseline Visit.

# 7.5 Procedure Visit

## 7.5.1 Sonendo GentleWave System Preparation

Prior to use of the Sonendo GentleWave System, the System and auxiliary equipment need to be prepared for treatment. Follow the Manufacturer's Operator's Manual and IFU for set-up of the System.

After the Sonendo GentleWave System is prepared, prepare for root canal therapy.

## 7.5.2 Root Canal Therapy Procedure Preparation

During RCT preparation, the PI should assess the subject tooth to determine if the tooth meets all of the Intra-Procedure Inclusion and none of the Intra-Procedure Exclusion Criteria. The RCT preparation is to be performed using standard endodontic practices.

- 1. Use of a dental bib is recommended.
- 2. Protective safety eyewear is required.
- 3. Anesthetize the subject tooth and surrounding area.

Note: If at any stage throughout RCT preparation, the subject expresses pain, sensitivity or discomfort, the PI may provide more anesthetic per standard practice.

- 4. Isolate the subject tooth by placing a rubber dam.
- 5. If using an Occlusal Plate, it is recommended to clamp the distal adjacent tooth, if a distal adjacent tooth is present. If using a Tooth Cap, it is recommended to clamp the subject tooth.
- 6. Use of a putty or caulking (i.e. OraSeal® (Ultradent) or equivalent) along the subject tooth and rubber dam interface for optimum isolation of the subject tooth is recommended.
- 7. The subject tooth may be disinfected (e.g. using chlorhexidine or betadine).
- Any caries and/or dental fillings (e.g. amalgam) on the subject tooth must be removed.
  If a crown, inlay or onlay is present, it does not require removal unless necessary for treatment or if caries and/or leakage are present below the crown, inlay or onlay.

Note: If there is tissue present that may affect caries removal and/or crown restoration, sear off the tissue according to standard dental practice.

9. Use of caries detector to ensure that all caries are removed even if caries are not visibly present or cannot be detected with a dental probe is recommended.

Note: Ensure that the tooth is restorable without a post and has adequate biological width for restoration after caries removal. If not, the patient will be considered a Screen Failure (see Section 7.6.1 Screen Failures).

10. When necessary, restore/build-up the missing subject tooth structure with permanent restorative and bonding materials. Ensure the permanent restorative material is fully cured prior to treatment with the GentleWave System.

Note: If there are any caries left, they will be removed by the Sonendo GentleWave System, and this can cause leakage. This leakage will require any build-up material to be removed and replaced. If a crown, inlay or onlay comes off prior to or during treatment, it is recommend that the entire tooth structure be re-built or the crown or inlay or onlay be re-cemented unless an adequate seal can be created.

11. Prepare a conservative endodontic access opening defined as a straight line path from the coronal orifice to the full working length per standard endodontic procedure. If a crown, inlay or onlay is present, the access opening may be performed through it as long as a caries detector is used post access.

Note: Make sure the endodontic access is performed properly (per standard practice, i.e. pulp horns are removed and there is sufficient exposure of the pulpal cavity and floor).

# 7.5.3 Orifice Negotiation

Orifice negotiation for the study is defined as locating, accessing, finding or negotiating through the orifice of each canal.

- 1. Locate the orifices of each canal of the subject tooth.
  - a. Ultra-sonic and sonic devices may be used for removal of calcification and/or orifices negotiation.
  - b. Use of lasers is not permitted for the study.

Note: Use of orifice openers or Gates Glidden are allowed for tortuous or heavily calcified canals.

*Note: If laser devices are used the patient will be considered a Screen Failure as this meets Intra-Procedure Exclusion for the study.* 

# 7.5.4 Minimal Shaping

- 1. Prior to starting the minimal instrumentation process, it is recommended to utilize PA radiographs or cone beam to estimate the length of each root.
- 2. A syringe of  $\geq$  0.5% NaOCI along with lubrication during the minimal shaping process is required according to standard of care.
- 3. Gain patency. Use of a 6, 8, or 10 hand file to gain patency along with an apex locator is required per standard of care. Patency for use with the Sonendo GentleWave System is defined as 0.5mm from the apical foramen.
- 4. Use of an endodontic ruler to ensure no apical penetration throughout the instrumentation process is required per standard of care.

Note: There should be no apical penetration of any subject teeth. If apical penetration occurs on an upper subject tooth, the patient will be considered as a Screen Fail (see Section 7.6.1 Screen Failures).

5. Removal of calcification is recommended. Ultra-sonic and sonic devices may be used for removal of calcification

Radiographic verification of the working length for each canal using a Gutta Percha or size 10 or 15 file is recommended.

Note: There should be no apical penetration of any subject teeth. If apical penetration occurs on an upper subject tooth, the patient will be considered as a Screen Fail (see Section 7.6.1 Screen Failures).

6. Minimal shaping the canals to a maximum hand files size 25.02 is required.

Note: There should be no apical penetration of any subject teeth. If apical penetration occurs on an upper subject tooth, the patient will be considered as a Screen Fail (see Section 7.6.1 Screen Failures).

 Minimal shaping of all canals using rotary file size to a maximum of 25.08 is required. The Master Apical File (MAF) is defined for the study as the final apical file.

Note: There should be no apical penetration of any subject teeth. If apical penetration occurs on an upper subject tooth, the patient will be considered as a Screen Fail (see Section 7.6.1 Screen Failures).

8. Continue with Sonendo GentleWave System preparation (*see Section 7.7 Sonendo GentleWave System Treatment*).

